Internal medicine/family medicine visits (30 days prior); n (%)	8,667 (51.8%)	8,658 (51.7%)	15,681 (67.4%)	15,619 (67.1%)	17,442 (60.5%)	17,316 (60.0%)	41,790 (60.7%)	41,593 (60.4%)	0.01
Internal medicine/family medicine visits (31 to 180 days prior); n (%)	10,237 (61.2%)	10,229 (61.1%)	17,149 (73.7%)	17,062 (73.3%)	21,118 (73.2%)	21,055 (73.0%)	48,504 (70.4%)	48,346 (70.2%)	0.00
Cardiologist visit; n (%)	3,197 (19.1%)	3,226 (19.3%)	3,866 (16.6%)	3,917 (16.8%)	8,193 (28.4%)	8,255 (28.6%)	15,256 (22.2%)	15,398 (22.4%)	0.00
Number of Cardiologist visits (30 days prior); n (%)	990 (5.9%)	1,022 (6.1%)	1,192 (5.1%)	1,175 (5.1%)	2,541 (8.8%)	2,563 (8.9%)	4,723 (6.9%)	4,760 (6.9%)	0.00

Table 1

Number of Cardiologist visits (31 to 180 days prior); n (%)	2,698 (16.1%)	2,721 (16.3%)	3,272 (14.1%)	3,308 (14.2%)	7,110 (24.6%)	7,144 (24.8%)	13,080 (19.0%)	13,173 (19.1%)	0.00
Electrocardiogram ; n (%)	3,814 (22.8%)	3,833 (22.9%)	5,351 (23.0%)	5,482 (23.6%)	8,209 (28.5%)	8,398 (29.1%)	17,374 (25.2%)	17,713 (25.7%)	-0.01
Use of glucose test strips; n (%)	578 (3.5%)	584 (3.5%)	926 (4.0%)	953 (4.1%)	932 (3.2%)	953 (3.3%)	2,436 (3.5%)	2,490 (3.6%)	-0.01
Dialysis; n (%)	0 (0.0%)	0 (0.0%)	0 (0.0%)	0 (0.0%)	0 (0.0%)	0 (0.0%)	000 (0.0%)	000 (0.0%)	#DIV/0!
Naive new user v8 Copy; n (%)	1,847 (11.0%)	1,869 (11.2%)	1,991 (8.6%)	2,032 (8.7%)	1,870 (6.5%)	1,975 (6.8%)	5,708 (8.3%)	5,876 (8.5%)	-0.01
N antidiabetic drugs at index date Copy ...mean (sd)	2.26 (0.88)	2.26 (0.86)	2.32 (0.90)	2.32 (0.88)	2.33 (0.89)	2.35 (0.88)	2.31 (0.89)	2.32 (0.88)	-0.01
...median [IQR]	2.00 [2.00, 3.00]	2.00 [2.00, 3.00]	2.00 [2.00, 3.00]	2.00 [2.00, 3.00]	2.00 [2.00, 3.00]	2.00 [2.00, 3.00]	2.00 [2.00, 3.00]	2.00 [2.00, 3.00]	0.00
number of different/distinct medication prescriptions									
...mean (sd)	9.99 (4.51)	9.95 (4.43)	9.68 (4.21)	9.71 (4.16)	10.40 (4.33)	10.45 (4.40)	10.06 (4.33)	10.08 (4.33)	0.00
...median [IQR]	9.00 [7.00, 12.00]	9.00 [7.00, 12.00]	9.00 [7.00, 12.00]	9.00 [7.00, 12.00]	10.00 [7.00, 13.00]	10.00 [7.00, 13.00]	9.42 (4.33)	9.42 (4.33)	0.00
Number of Hospitalizations									
...mean (sd)	0.03 (0.24)	0.03 (0.17)	0.02 (0.15)	0.02 (0.16)	0.04 (0.23)	0.04 (0.23)	0.03 (0.21)	0.03 (0.19)	0.00
...median [IQR]	0.00 [0.00, 0.00]	0.00 [0.00, 0.00]	0.00 [0.00, 0.00]	0.00 [0.00, 0.00]	0.00 [0.00, 0.00]	0.00 [0.00, 0.00]	0.00 (0.21)	0.00 (0.19)	0.00
Number of hospital days									
...mean (sd)	0.12 (1.00)	0.12 (0.97)	0.09 (0.81)	0.10 (0.88)	0.22 (1.56)	0.23 (1.87)	0.15 (1.22)	0.16 (1.40)	-0.01
...median [IQR]	0.00 [0.00, 0.00]	0.00 [0.00, 0.00]	0.00 [0.00, 0.00]	0.00 [0.00, 0.00]	0.00 [0.00, 0.00]	0.00 [0.00, 0.00]	0.00 (1.22)	0.00 (1.40)	0.00
Number of Emergency Department (ED) visits									
...mean (sd)	0.21 (0.72)	0.21 (0.76)	0.04 (0.74)	0.04 (0.55)	0.31 (0.95)	0.31 (1.07)	0.19 (0.83)	0.19 (0.85)	0.00
...median [IQR]	0.00 [0.00, 0.00]	0.00 [0.00, 0.00]	0.00 [0.00, 0.00]	0.00 [0.00, 0.00]	0.00 [0.00, 0.00]	0.00 [0.00, 0.00]	0.00 (0.83)	0.00 (0.85)	0.00
Number of Office visits									
...mean (sd)	4.29 (3.42)	4.24 (3.06)	4.23 (3.30)	4.21 (3.07)	5.08 (3.83)	5.08 (3.60)	4.60 (3.56)	4.58 (3.30)	0.01
...median [IQR]	3.00 [2.00, 6.00]	3.00 [2.00, 6.00]	3.00 [2.00, 5.00]	3.00 [2.00, 5.00]	4.00 [2.00, 7.00]	4.00 [3.00, 7.00]	3.42 (3.56)	3.42 (3.30)	0.00
Number of Endocrinologist visits									
...mean (sd)	0.77 (2.73)	0.85 (3.12)	0.72 (2.61)	0.87 (3.27)	1.08 (4.08)	1.22 (4.66)	0.88 (3.33)	1.01 (3.88)	-0.04
...median [IQR]	0.00 [0.00, 0.00]	0.00 [0.00, 0.00]	0.00 [0.00, 0.00]	0.00 [0.00, 0.00]	0.00 [0.00, 0.00]	0.00 [0.00, 0.00]	0.00 (3.33)	0.00 (3.88)	0.00
Number of internal medicine/family medicine visits									
...mean (sd)	7.13 (11.56)	7.03 (10.98)	6.26 (7.11)	6.46 (7.42)	7.46 (10.23)	7.75 (9.99)	6.97 (9.67)	7.14 (9.47)	-0.02
...median [IQR]	4.00 [0.00, 9.00]	4.00 [0.00, 9.00]	4.00 [2.00, 8.00]	4.00 [2.00, 9.00]	4.00 [2.00, 10.00]	5.00 [2.00, 10.00]	4.00 (9.67)	4.42 (9.47)	-0.04
Number of Cardiologist visits									
...mean (sd)	0.78 (2.61)	0.76 (2.44)	0.61 (2.04)	0.63 (2.14)	1.33 (3.71)	1.35 (3.65)	0.95 (2.97)	0.96 (2.93)	0.00
...median [IQR]	0.00 [0.00, 0.00]	0.00 [0.00, 0.00]	0.00 [0.00, 0.00]	0.00 [0.00, 0.00]	0.00 [0.00, 1.00]	0.00 [0.00, 1.00]	0.00 (2.97)	0.00 (2.93)	0.00
Number of electrocardiograms received									
...mean (sd)	0.36 (0.86)	0.36 (0.86)	0.35 (0.82)	0.35 (0.83)	0.50 (1.05)	0.50 (1.07)	0.42 (0.93)	0.42 (0.94)	0.00
...median [IQR]	0.00 [0.00, 0.00]	0.00 [0.00, 0.00]	0.00 [0.00, 0.00]	0.00 [0.00, 0.00]	0.00 [0.00, 1.00]	0.00 [0.00, 1.00]	0.00 (0.93)	0.00 (0.94)	0.00
Number of HbA1c tests ordered									
...mean (sd)	1.36 (0.89)	1.35 (0.87)	1.28 (0.88)	1.28 (0.85)	1.56 (0.90)	1.56 (0.82)	1.42 (0.89)	1.41 (0.84)	0.01
...median [IQR]	1.00 [1.00, 2.00]	1.00 [1.00, 2.00]	1.00 [1.00, 2.00]	1.00 [1.00, 2.00]	2.00 [1.00, 2.00]	2.00 [1.00, 2.00]	1.42 (0.89)	1.42 (0.84)	0.00
Number of glucose tests ordered									
...mean (sd)	0.43 (1.87)	0.43 (1.71)	0.39 (1.63)	0.39 (1.03)	0.47 (1.34)	0.47 (1.11)	0.43 (1.58)	0.43 (1.26)	0.00
...median [IQR]	0.00 [0.00, 0.00]	0.00 [0.00, 0.00]	0.00 [0.00, 0.00]	0.00 [0.00, 0.00]	0.00 [0.00, 0.00]	0.00 [0.00, 0.00]	0.00 (1.58)	0.00 (1.26)	0.00
Number of lipid tests ordered									
...mean (sd)	1.06 (0.96)	1.06 (0.94)	1.06 (1.29)	1.06 (1.13)	1.13 (0.88)	1.13 (0.83)	1.09 (1.05)	1.09 (0.97)	0.00
...median [IQR]	1.00 [0.00, 2.00]	1.00 [0.00, 2.00]	1.00 [0.00, 1.00]	1.00 [0.00, 2.00]	1.00 [0.00, 2.00]	1.00 [0.00, 2.00]	1.00 (1.05)	1.00 (0.97)	0.00
Number of creatinine tests ordered									
...mean (sd)	0.03 (0.22)	0.03 (0.20)	0.03 (0.23)	0.04 (0.24)	0.07 (0.34)	0.07 (0.32)	0.05 (0.28)	0.05 (0.27)	0.00
...median [IQR]	0.00 [0.00, 0.00]	0.00 [0.00, 0.00]	0.00 [0.00, 0.00]	0.00 [0.00, 0.00]	0.00 [0.00, 0.00]	0.00 [0.00, 0.00]	0.00 (0.28)	0.00 (0.27)	0.00
Number of BUN tests ordered									
...mean (sd)	0.02 (0.16)	0.02 (0.16)	0.02 (0.18)	0.02 (0.18)	0.04 (0.28)	0.04 (0.26)	0.03 (0.22)	0.03 (0.21)	0.00
...median [IQR]	0.00 [0.00, 0.00]	0.00 [0.00, 0.00]	0.00 [0.00, 0.00]	0.00 [0.00, 0.00]	0.00 [0.00, 0.00]	0.00 [0.00, 0.00]	0.00 (0.22)	0.00 (0.21)	0.00
Number of tests for microalbuminuria									
...mean (sd)	0.84 (1.19)	0.85 (1.18)	0.74 (1.11)	0.74 (1.10)	0.53 (0.73)	0.54 (0.73)	0.68 (0.99)	0.68 (0.99)	0.00
...median [IQR]	0.00 [0.00, 2.00]	0.00 [0.00, 2.00]	0.00 [0.00, 2.00]	0.00 [0.00, 2.00]	0.00 [0.00, 1.00]	0.00 [0.00, 1.00]	0.00 (0.99)	0.00 (0.99)	0.00
Total N distinct ICD9/ICD10 diagnoses at the 3rd digit level Copy									
...mean (sd)	5.56 (5.86)	5.43 (6.00)	2.09 (3.20)	2.05 (3.27)	5.91 (6.84)	5.82 (6.92)	4.53 (5.60)	4.45 (5.69)	0.01
...median [IQR]	5.00 [0.00, 8.00]	5.00 [0.00, 8.00]	0.00 [0.00, 4.00]	0.00 [0.00, 4.00]	4.00 [0.00, 9.00]	4.00 [0.00, 9.00]	2.89 (5.60)	2.89 (5.69)	0.00
Use of thiazide; n (%)	2,040 (12.2%)	2,060 (12.3%)	2,782 (12.0%)	2,737 (11.8%)	4,125 (14.3%)	4,100 (14.2%)	8,947 (13.0%)	8,897 (12.9%)	0.00
Use of beta blockers; n (%)	6,033 (36.0%)	6,038 (36.1%)	8,159 (35.1%)	8,198 (35.2%)	13,867 (48.1%)	13,913 (48.2%)	28,059 (40.8%)	28,149 (40.9%)	0.00
Use of calcium channel blockers; n (%)	4,836 (28.9%)	4,820 (28.8%)	6,641 (28.5%)	6,697 (28.8%)	9,762 (33.8%)	9,796 (34.0%)	21,239 (30.8%)	21,313 (31.0%)	0.00

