5.1 Cohort Summary

This study will involve a new user, parallel group, cohort study design comparing canagliflozin to the DPP-4 inhibitor (DPP4i) antidiabetic class. DPP4is serve as a proxy for placebo, since this class of antidiabetic drugs is not known to have an impact on the outcome of interest. The comparison against DPP4 inhibitors is the **primary comparison**. Initiators of 2nd generation sulfonylureas are used as a secondary comparator group. The patients will be required to have continuous enrollment during the baseline period of 180 days before initiation of canagliflozin or a comparator drug (cohort entry date). Follow-up for the outcome (3P-MACE), begins the day after drug initiation. As in the trial, patients are allowed to take other antidiabetic medications during the study.

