Excluded based on Exclusion 14- History of Malignant Neoplasm (prior 5 years)	-4,554	121,487	-3,985	132,537	-19,311	315,535
Excluded based on Exclusion 15- HIV/AIDS (dx and meds) -prior 5 years	-64	121,423	-56	132,481	-127	315,408
Excluded based on Exclusion 16- Hematological disorder	-1,540	119,883	-1,633	130,848	-7,624	307,784
Excluded based on Exclusion 17- CCI (180 days) >=10	-177	119,706	-50	130,798	-696	307,088

Excluded based on Exclusion 18 - Major Surgery (90 days prior)	-191	119,515	-212	130,586	-674	306,414
Excluded based on Exclusion 20- Use of SGLT2i (prior 6 months)	-833	118,682	-892	129,694	-817	305,597
Excluded based on Exclusion 22- use of a corticosteroid medication or immunosuppressive agent	-3,235	115,447	-3,085	126,609	-8,985	296,612
Excluded based on Exclusion 23- Use of cana in prior 3 months (although this is already applied as part of cohort creation)	0	115,447	0	126,609	0	296,612
Excluded based on Exclusion 24- Alcohol or Drug abuse (prior 3 years) and Exclusion 25- Pregnancy	-972	114,475	-532	126,077	-1,766	294,846
Final cohort		114,475		126,077		294,846

* Medicare database includes only patients with at least one diagnosis for diabetes, heart failure, or cerebrovascular disease.

**Exclusion 24 and 25 collapsed to adhere to CMS cell suppression guidelines.

For canagliflozin vs. 2nd generation SUs

	Optum		MarketScan		Medicare*	
	Less Excluded Patients	Remaining Patients	Less Excluded Patients	Remaining Patients	Less Excluded Patients	Remaining Patients
All patients		74,864,884		191,990,035		23,466,175
Patients who used exposure or a reference between April 1, 2013 to Dec 2017 (for MarketScan/Medicare)/March 2019 (for Optum)	-73,662,096	1,202,788	-190,768,942	1,221,093	-20,351,733	3,114,442
Patients who have continuous 6 months registration in the database	-165,247	1,037,541	-115,162	1,105,931	-861,454	2,252,988
Patients without prior use of reference	-710,706	326,835	-759,153	346,778	-1,627,827	625,161
Patients without prior use of exposure	-70,933	255,902	-88,833	257,945	-68,783	556,378
Excluded because patient qualified in >1 exposure category	-168	255,734	-149	257,796	-118	556,260
Excluded based on Age	-10	255,724	0	257,796	0	556,260
Excluded based on Gender	-17	255,707	0	257,796	0	556,260
Excluded based on Inclusion 1- DM Type 2 with ICD-10	-14,479	241,228	-23,583	234,213	-8,608	547,652

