Final cohort		172,234		156,544		415,696

* Medicare database includes only patients with at least one diagnosis for diabetes, heart failure, or cerebrovascular disease.

** Exclusion 24 and 25 collapsed to adhere to CMS cell suppression guidelines.

6. Variables

6.1 Exposure-related variables:

Study drug:

The study exposure of interest is initiation of canagliflozin. Initiation will be defined by no use of any SGLT-2 inhibitor or a comparator in the prior 6 months before treatment initiation (washout period).

Comparator agents:

- Initiators of canagliflozin will be compared to initiators of-
 - DPP4i (**primary**)
 - 2nd generation sulfonylureas

Because canagliflozin and comparators are frequently used as second or third line treatments of T2DM, we expect it to be unlikely that canagliflozin and comparators are initiated in patients with substantially different baseline risk for proposed outcomes.

6.2 Preliminary Covariates:

- Age
- Sex
- Combined Comorbidity Index (CCI), measured over the default baseline covariate assessment period, defined as 180 days prior to and including index date

Covariates listed above represent only a small subset of covariates that will ultimately be controlled for in the design and analysis. We use the covariates above only for initial feasibility analyses to judge whether there is likely to be sufficient overlap between treatment groups to proceed with the study. Remaining covariates are defined only after the study has passed the initial feasibility analysis and the initial power assessment and are listed in Table 1 (**Appendix B**). These covariates are based on those used by Patorno et al. (2019).

6.3 Outcome variables and study follow-up:

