Action report name:

For canagliflozin vs. DPP4i

- Optum- <https://bwh-dope.aetion.com/projects/details/660/results/44837/result/0>
- Marketscan- <https://bwh-dope.aetion.com/projects/details/661/results/44838/result/0>
- Medicare- <https://bwh-dope.aetion.com/projects/details/662/results/44839/result/0>

For canagliflozin vs. 2nd generation SUs

- Optum- <https://bwh-dope.aetion.com/projects/details/660/results/44834/result/0>
- Marketscan- <https://bwh-dope.aetion.com/projects/details/661/results/44835/result/0>
- Medicare- <https://bwh-dope.aetion.com/projects/details/662/results/44836/result/0>

Date conducted: 11/18/2019

After review of initial feasibility and power analyses, complete creation of the remaining covariates (see Table 1 below for list of covariates). Again, using the dummy outcome of a 90-day gap in database enrollment, complete a 1:1 PS-matched analysis. The PS should include the complete list of covariates (excluding laboratory values, which are missing in some patients).

- Provide plot of PS distributions stratified by treatment group.

Note- Please refer to **Appendix B**.

- Report covariate balance after matching.

Note- For Table 1, please refer to **Appendix B**.

- Report reasons for censoring by treatment group.

- For canagliflozin vs. DPP4i

	Overall	Referent	Exposure
Dummy Outcome	0 (0.00%)	0 (0.00%)	0 (0.00%)
Death	589 (0.39%)	374 (0.49%)	215 (0.28%)
Start of an additional exposure	6,913 (4.54%)	2,413 (3.17%)	4,500 (5.91%)
End of index exposure	98,215 (64.53%)	47,931 (62.98%)	50,284 (66.08%)
Specified date reached	22,353 (14.69%)	12,162 (15.98%)	10,191 (13.39%)
End of patient enrollment	19,170 (12.60%)	9,407 (12.36%)	9,763 (12.83%)
Switch to other DPP4i (for censoring) + nursing home admission	4,962 (3.26%)	3,814 (5.01%)	1,148 (1.51%)

- For canagliflozin vs. 2nd generation SUs

	Overall	Referent	Exposure
Dummy Outcome	0 (0.00%)	0 (0.00%)	0 (0.00%)
Death	548 (0.40%)	364 (0.53%)	184 (0.27%)
Start of an additional exposure	6,001 (4.36%)	1,842 (2.68%)	4,159 (6.04%)
End of index exposure	85,900 (62.38%)	41,024 (59.58%)	44,876 (65.18%)
Specified date reached	22,281 (16.18%)	12,957 (18.82%)	9,324 (13.54%)
End of patient enrollment	18,853 (13.69%)	9,660 (14.03%)	9,193 (13.35%)
Switch to other SUs (for censoring) + nursing home admission	4,117 (2.99%)	3,003 (4.36%)	1,114 (1.62%)

- Report follow-up time by treatment group.

- For canagliflozin vs. DPP4i

Median Follow-Up Time (Days) [IQR]			

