...mean (sd)	174.40 (73.35)	178.35 (69.83)	182.10 (77.32)	175.89 (63.14)	N/A	N/A	175.26 (73.81)	177.96 (68.82)
...median [IQR]	156.00 [126.00, 203.00]	162.00 [130.00, 211.00]	162.00 [130.00, 215.00]	163.00 [131.50, 208.00]	N/A	N/A	156.67 (73.81)	162.16 (68.82)
...Missing: n (%)	96,334 (62.2%)	9,763 (56.9%)	124,653 (94.4%)	22,925 (94.3%)	N/A	N/A	220,987 (77.0%)	32,688 (78.8%)
Lab result number- Potassium mean (only 1-7 included)	60,268	7,541	7,444	1,371	N/A	N/A	67,712	8,912
...mean (sd)	4.46 (0.44)	4.44 (0.40)	4.32 (0.46)	4.36 (0.41)	N/A	N/A	4.44 (0.44)	4.43 (0.40)
...median [IQR]	4.45 [4.20, 4.70]	4.40 [4.20, 4.70]	4.30 [4.00, 4.60]	4.38 [4.10, 4.60]	N/A	N/A	4.43 (0.44)	4.40 (0.40)
...Missing: n (%)	94,618 (61.1%)	9,613 (56.0%)	124,596 (94.4%)	22,947 (94.4%)	N/A	N/A	219,214 (76.4%)	32,560 (78.5%)
Comorbidity Scores								
CCI (180 days)- ICD9 and ICD10								
...mean (sd)	2.48 (1.68)	2.06 (1.28)	1.84 (1.27)	1.65 (0.97)	2.61 (1.79)	2.37 (1.51)	2.43 (1.67)	2.05 (1.29)
...median [IQR]	2.00 [1.00, 3.00]	2.00 [1.00, 2.00]	1.00 [1.00, 2.00]	1.00 [1.00, 2.00]	2.00 [1.00, 4.00]	2.00 [1.00, 3.00]	1.80 (1.67)	1.65 (1.29)
Frailty Score: Qualitative Version 365 days as Categories, ...0; n (%)	97,586 (63.0%)	11,069 (64.5%)	71,771 (54.4%)	12,999 (53.5%)	159,513 (41.4%)	13,058 (45.0%)	328,870 (48.9%)	37,126 (52.7%)
...1 to 2; n (%)	42,109 (27.2%)	4,734 (27.6%)	45,704 (34.6%)	9,121 (37.5%)	136,252 (35.4%)	10,120 (34.9%)	224,065 (33.3%)	23,975 (34.0%)
...3 or more; n (%)	15,191 (9.8%)	1,351 (7.9%)	14,565 (11.0%)	2,198 (9.0%)	89,667 (23.3%)	5,809 (20.0%)	119,423 (17.8%)	9,358 (13.3%)
Frailty Score: Empirical Version 365 days as Categories, ...<0.12908; n (%)	43,729 (28.2%)	5,999 (35.0%)	38,804 (29.4%)	8,113 (33.4%)	51,925 (13.5%)	4,669 (16.1%)	134,458 (20.0%)	18,781 (26.7%)
...0.12908 - 0.1631167; n (%)	55,491 (35.8%)	6,402 (37.3%)	50,669 (38.4%)	9,645 (39.7%)	111,334 (28.9%)	8,922 (30.8%)	217,494 (32.3%)	24,969 (35.4%)
...>=0.1631167; n (%)	55,666 (35.9%)	4,753 (27.7%)	42,567 (32.2%)	6,560 (27.0%)	222,173 (57.6%)	15,396 (53.1%)	320,406 (47.7%)	26,709 (37.9%)
Non-Frailty; n (%)	86,446 (55.8%)	9,990 (58.2%)	65,874 (49.9%)	13,103 (53.9%)	20,611 (5.3%)	1,336 (4.6%)	172,931 (25.7%)	24,429 (34.7%)
Frailty Score (mean): Qualitative Version 365 days, ...mean (sd)	0.78 (1.42)	0.67 (1.20)	0.91 (1.42)	0.83 (1.20)	1.53 (1.95)	1.32 (1.69)	1.24 (1.74)	0.99 (1.42)

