Diabetes with unspecified complication; n (%)	836 (5.0%)	814 (4.9%)	988 (4.2%)	990 (4.3%)	1,526 (5.3%)	1,517 (5.3%)	3,350 (4.9%)	3,321 (4.8%)	3,321 (4.8%)	0.00
Diabetes mellitus without mention of complications; n (%)	14,237 (85.0%)	14,249 (85.1%)	21,402 (92.0%)	21,452 (92.2%)	26,407 (91.5%)	26,443 (91.7%)	62,046 (90.1%)	62,144 (90.3%)	62,144 (90.3%)	-0.01
Hypertension: 1 inpatient or 2 outpatient claims within 365 days; n (%)	15,348 (91.7%)	15,341 (91.6%)	20,375 (87.6%)	20,341 (87.4%)	27,592 (95.7%)	27,624 (95.8%)	63,315 (92.0%)	63,306 (91.9%)	63,306 (91.9%)	0.00
Hyperlipidemia; n (%)	12,921 (77.2%)	12,951 (77.4%)	17,546 (75.4%)	17,573 (75.5%)	23,820 (82.6%)	23,824 (82.6%)	54,287 (78.8%)	54,348 (78.9%)	54,348 (78.9%)	0.00
Edema; n (%)	721 (4.3%)	741 (4.4%)	728 (3.1%)	727 (3.1%)	2,166 (7.5%)	2,095 (7.3%)	3,615 (5.3%)	3,563 (5.2%)	3,563 (5.2%)	0.00
Renal Dysfunction (non-diabetic); n (%)	1,611 (9.6%)	1,605 (9.6%)	1,291 (5.5%)	1,199 (5.2%)	3,614 (12.5%)	3,519 (12.2%)	6,516 (9.5%)	6,323 (9.2%)	6,323 (9.2%)	0.01
Occurrence of acute renal disease; n (%)	146 (0.9%)	135 (0.8%)	89 (0.4%)	92 (0.4%)	300 (1.0%)	320 (1.1%)	535 (0.8%)	547 (0.8%)	547 (0.8%)	0.00
Occurrence of chronic renal insufficiency; n (%)	1,286 (7.7%)	1,321 (7.9%)	910 (3.9%)	861 (3.7%)	2,943 (10.2%)	2,882 (10.0%)	5,139 (7.5%)	5,064 (7.4%)	5,064 (7.4%)	0.00
Chronic kidney disease; n (%)	1,211 (7.2%)	1,235 (7.4%)	834 (3.6%)	743 (3.2%)	2,753 (9.5%)	2,646 (9.2%)	4,798 (7.0%)	4,624 (6.7%)	4,624 (6.7%)	0.01
CKD Stage 3-4; n (%)	628 (3.8%)	635 (3.8%)	398 (1.7%)	370 (1.6%)	1,538 (5.3%)	1,534 (5.3%)	2,564 (3.7%)	2,539 (3.7%)	2,539 (3.7%)	0.00
Occurrence of hypertensive nephropathy; n (%)	553 (3.3%)	537 (3.2%)	283 (1.2%)	295 (1.3%)	990 (3.4%)	1,006 (3.5%)	1,826 (2.7%)	1,838 (2.7%)	1,838 (2.7%)	0.00
Occurrence of miscellaneous renal insufficiency; n (%)	318 (1.9%)	314 (1.9%)	375 (1.6%)	368 (1.6%)	1,003 (3.5%)	1,026 (3.6%)	1,696 (2.5%)	1,708 (2.5%)	1,708 (2.5%)	0.00
Glaucoma or cataracts; n (%)	2,814 (16.8%)	2,806 (16.8%)	3,187 (13.7%)	3,120 (13.4%)	7,913 (27.4%)	7,842 (27.2%)	13,914 (20.2%)	13,768 (20.0%)	13,768 (20.0%)	0.00
Cellulitis or abscess of toe; n (%)	176 (1.1%)	146 (0.9%)	129 (0.6%)	132 (0.6%)	332 (1.2%)	306 (1.1%)	637 (0.9%)	584 (0.8%)	584 (0.8%)	0.01
Foot ulcer; n (%)	217 (1.3%)	205 (1.2%)	233 (1.0%)	255 (1.1%)	542 (1.9%)	556 (1.9%)	992 (1.4%)	1,016 (1.5%)	1,016 (1.5%)	-0.01
Bladder stones; n (%)	11 (0.1%)	12 (0.1%)	24 (0.1%)	16 (0.1%)	41 (0.1%)	37 (0.1%)	076 (0.1%)	065 (0.1%)	065 (0.1%)	0.00

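### Both frailty scores in the propensity score look back 365 days, but cohort entry guarantees only 180 days of enrolment, and observed enrolment length is neither reported nor matched on

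*Combined protocol and SAP*

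**What the plan says.** Section 5.1 states: "The patients will be required to have continuous enrollment during the baseline period of 180 days" before initiation. Both flowcharts in Section 5.3 apply the same filter: "Patients who have continuous 6 months registration in the database". Section 6.2 sets the default covariate window through the comorbidity index (CCI), which is "measured over the default baseline covariate assessment period, defined as 180 days prior to and including index date".

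Section 9 then specifies the matching model: "The PS should include the complete list of covariates", with laboratory values excepted.

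Under Comorbidity Scores, Table 1 of Appendix B lists "Frailty Score: Qualitative Version 365 days as Categories" and an empirical frailty score also labelled 365 days. Each appears as categories and as a mean. These rows are in the DPP4i table and the SU table, before and after matching. The CCI in the same block is labelled 180 days. Neither table has a row for length of observed enrolment, and no section says how days 181 to 365 are handled for a patient not enrolled then.

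**The concern.** A patient can enter the cohort with as little as 180 days of history. For anyone enrolled 180 to 364 days, part of the frailty window cannot contain claims. If that part is read as a period without claims, the patient looks less frail than an identical patient with a full year on record.

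Two patients with the same recorded score but different observed history are then not equally frail, and the PS contains nothing that distinguishes them directly. The balance table still shows the score as balanced, and that table is what is examined at the stop-and-review step closing Section 10. If the share of short-enrolled patients differs between canagliflozin and comparator initiators, some frailty imbalance could remain unseen in the primary comparison as well as the secondary one.

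**Working it through.** **1. Windows side by side.** Guaranteed history: 180 days (Sections 5.1 and 5.3). CCI: 180 days (Section 6.2, Table 1). Both frailty scores: 365 days (Table 1, both comparators). Up to 365 − 180 = 185 days of the frailty window may be unobserved.

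**2. The plan's own balance figures.** The standardised difference for a binary level is (p1 − p2) / √[(p1q1 + p2q2)/2]. For qualitative frailty 3 or more, pooled, reference minus canagliflozin:

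| Comparison | Before matching | After matching |
|---|---|---|
| DPP4i | 80,640/450,742 vs 10,647/83,371: 0.142 | 9,820/76,101 vs 9,834/76,101: −0.001 |
| SU | 119,423/672,358 vs 9,358/70,459: 0.124 | 8,864/68,850 vs 9,170/68,850: −0.013 |

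The matched values agree with the printed 0.00 and −0.01. The recorded score is balanced.

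**3. Is anyone classed as unobserved?** For the unmatched SU reference group in Optum, the three qualitative categories give 97,586 + 42,109 + 15,191 = 154,886, exactly the cohort size. The same sum was checked for 2 scores × 2 comparators × unmatched and matched × 8 columns = 64 cells, and the difference was 0 each time. Laboratory-result rows have a missing line; frailty rows do not. So every patient is scored, whatever their enrolment length. Treating unobserved time as absence of claims is an inference from this, not something the plan states.

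**4. Possible size.** The share of patients with 180 to 364 days is not given, so corrected scores cannot be computed. The following is an illustration. Assumptions: a short-enrolled patient who is truly at 3 or more is recorded as such with probability c = 0.6; recorded prevalence after matching is 12.9% in both arms; the short-enrolled share f is 10% to 30%; c is the same in both matched arms. Then

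true prevalence = 0.129 / [1 − f(1 − c)] = 0.129 / (1 − 0.4f).

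This gives 0.1344 at f = 0.10, 0.1372 at 0.15, 0.1402 at 0.20 and 0.1466 at 0.30. If true frailty multiplies outcome risk by R, the crude risk ratio is multiplied by [1 + p_exp(R − 1)] / [1 + p_ref(R − 1)].

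| f reference / exposed | Hidden standardised difference | Multiplier, R = 2 | Multiplier, R = 3 |
|---|---|---|---|
| 0.20 / 0.20 | 0 | 1.000 | 1.000 |
| 0.10 / 0.15 | −0.008 | 1.0025 | 1.0045 |
| 0.10 / 0.20 | −0.017 | 1.0052 | 1.0092 |
| 0.30 / 0.20 | 0.018 | 0.9944 | 0.9901 |

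A 5 to 10 point difference in short enrolment moves a crude risk ratio by roughly 0.3% to 1.0%, in either direction.

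**The case against.** The best defence is that using all available history is a reasonable choice and the consequence is trivial. The plan does the same elsewhere: some exclusions look back 1095 or 1825 days behind the same six-month filter. The PS also holds many correlates of frailty not labelled 365 days, such as the 180-day CCI, hospitalisations, hospital days, emergency visits, falls, fractures, dementia and medication count. Their pooled matched differences are 0.01 or less in absolute value. This stands as mitigation and is the main reason to rate the point low. It does not show what the enrolment distribution is in each arm.

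Several stronger readings are tempting, and the documents do not support them:

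- **Hypertension has the same fault.** The row "Hypertension: 1 inpatient or 2 outpatient claims within 365 days" can mean two claims within a year of each other rather than a one-year look-back. It also hardly differs before matching (recomputed 0.037 against DPP4i, −0.015 against SU).
- **The six-month filter shows how many windows are truncated.** In the SU comparison it removed 165,247/1,202,788 = 13.7% (Optum), 115,162/1,221,093 = 9.4% (MarketScan) and 861,454/3,114,442 = 27.7% (Medicare). Those are users before the washout; in Optum the next step removes a further 710,706 of 1,037,541. Nothing links that share to the share of remaining initiators with 180 to 364 days.
- **Truncation is visible across databases.** The qualitative mean among unmatched SU patients is lower in Optum (0.78) than MarketScan (0.91) although Optum patients are older. But the empirical score goes the other way: 35.9% against 32.2% in the top category.
- **Frailty is a dominant confounder here.** Its unmatched standardised difference is about 0.12 to 0.14, against 0.70 (DPP4i) and 0.76 (SU) for age.

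**Conclusion.** The mismatch holds for the two frailty scores, in the primary and the secondary comparison alike. For patients enrolled 180 to 364 days the score is probably truncated towards less frail, and the matched balance reported for it is balance on the truncated measure. This rests on one inference, that unobserved time counts as no claims, which the complete scoring of every patient supports well. The windows in the Section 4 design diagram could not be checked, because the figure was not available.

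The effect is likely small: about 0.3% to 1.0% on a crude risk ratio under the illustration's assumptions. It is zero if enrolment length does not differ by arm, provided the captured fraction is also the same in the matched arms. A reader might infer that the planned hazard ratio is materially biased; nothing in the documents supports that. This is a minor improvement to specification and reporting.

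**What to change.** Before the comparative analyses in Section 13, derive one covariate: days of continuous enrolment observed in the 365 days up to index, ranging from 180 to 365. Add it to the PS and to Table 1 for both comparators, report it by arm in each database and pooled, and re-run the match. State in the Table 1 notes how the frailty scores treat days without enrolment.

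This lets matching balance the degree of truncation; it does not recover the unobserved history. The cost is one derived variable and a re-match in three databases for two comparators, with balance tables and matched counts refreshed. No new data are needed. The date field in Section 13 is blank in this version, so the change can be made before any comparative result is seen.

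Recomputing frailty on 180 days is not proposed as the remedy. It would discard real history for long-enrolled patients, and the empirical cut-points (0.12908 and 0.1631167) are given only for the 365-day version.
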